## 6.2 ICD-10 codes for relevant metrics

Description	ICD-10

 
1. Must be in 1st or 2nd diagnosis and must not be chronic, or
 
	

 
2. If patient is admitted, must be in 1st or 2nd diagnosis on hospital discharge.
 
	
Infection and inflammatory reaction due to internal prosthetic device, implant, and graft 
 
• Due to unspecified implant, device, and graft
 
• Due to internal joint prosthesis
 
• Due to other internal orthopedic device, implant and graft
 
	T8579XA T8450XA T8460XA
Other complications of internal prosthetic device, implant, and graft 
 
• Due to unspecified implant, device, and graft
 
• Due to internal joint prosthesis
 
• Due to other internal orthopedic device, implant, and graft
 
	T859XXA T8481XA- T8486XA; T8489XA; T849XXA
Postoperative infection 
 
• Other post-operative infection (abscess, septicemia)
 
	K6811 T814XXA
Disruption of wound 
 
• Dehiscence of operation wound
 
	T8130XA- T8132XA
Infections of Skin and Subcutaneous Tissue 
 
• Upper arm and forearm
 
• Leg except foot
 
• Abscess NOS, Cellulitis NOS
 
	LO3119 LO3129 LO390 LO391
Gastrointestinal hemorrhage 
 
• Hematemesis
 
• Melena
 
• Hemorrhage of gastrointestinal tract, unspecified
 
	K920 K921 K922
Hemorrhage NOS	R58
Venous embolism and thrombosis of deep vessels of lower extremity 
 
• Of unspecified site
 
	I82409 I8291
Pulmonary embolism and infarction	I2690 I2692 I2699 T82817A, T82818A
Since ED coding is often not as precise as the above, we will likely need to also have these below	
Fever unspecified	R502 R509 R5081- R5094 R6883
Systemic inflammatory response syndrome due to infectious process without acute organ dysfunction	A419
Severe sepsis	R6520
Joint Replacement DRGs	461-462, 469-470
Hip and Knee specific DRGs	466-468, 488-489

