## 6. Appendix

### 6.1 Study Metrics

Metric	Justification
Patient Reported satisfaction – VAS and PPE-15	-Substantial opportunity for the Cleveland Clinic to differentiate itself among health systems and enhance revenue associated with patient satisfaction measures
Patient utilization and compliance	- Substantial opportunity for national exposure as related to national directives to drive patient engagement (See NCQA's Leadership Series: Focus on Patient Engagement at http://www.qualityprofiles.org/leadership_series/patient_engagement/index_patient_engagement.asp )
Physician and staff satisfaction	- Opportunity to demonstrate clinical adoption rates and low barriers to implementation.
Total 90 day post-operative cost from index date+1 (same day) or from index date + LOS (inpatient)*  *Claims submitted within 90 days must be limited to ICD-10 listed below (or if hospitalization due to ICD-10 below) in order to exclude unrelated claims.	Joint Coach templates should be able to either prevent the complication, or through early detection at the clinic level, reduce expense through minimized emergency room visits and readmissions.
30 day post-op hospitalization rate (this is a readmission if initially an inpatient procedure, or an admission if initially an outpatient procedure)*  *Must be associated with ICD-10s listed below in order to exclude unrelated readmissions.	
30-day ED Visit Rate*  *Must be associated with ICD-10s listed below in order to exclude unrelated ED visits.	
Number of follow up visits within 90 days	Demonstration to physicians and practices the potential to improve throughput and workflow efficiency by minimizing the number of follow up visits required.

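### Three code-restricted metrics in section 6.1 omit deep-vein thrombosis coded to a named vein, so they can be understated and the <4% hospitalization threshold becomes easier to meet

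*Combined protocol and SAP*

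**What the plan says.** Section 6.1 (Study Metrics) ties three starred metrics to the code list in section 6.2:

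- For the rate of hospitalization in the first 30 days, the note reads "Must be associated with ICD-10s listed below in order to exclude unrelated readmissions".
- Total 90-day cost has its own restriction, "Claims submitted within 90 days must be limited to ICD-10 listed below", which extends to hospitalizations caused by those codes.
- For the rate of ED visits over the same 30 days, the note reads "Must be associated with ICD-10s listed below in order to exclude unrelated ED visits".

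Section 6.2 adds a position rule. The code must be the first or second diagnosis and, for an admitted patient, must hold one of those positions at discharge. The first condition ("diagnosis and must not be chronic, or") also bars chronic diagnoses.

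The row for deep-vein events is headed "Venous embolism and thrombosis of deep vessels of lower extremity". Under it stands one sub-item, "Of unspecified site", and two codes, I82409 and I8291.

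A supplement for ED visits follows, introduced by "Since ED coding is often not as precise as the above, we will likely need to also have these below". It covers fever, systemic inflammatory response, severe sepsis and DRG groups.

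Section 6.3 sets a success threshold of <4% for the 30-day hospitalization rate, justified by a national average.

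**The concern.** The row heading names the condition in general, while the sub-item narrows it to cases with no recorded site. Because section 6.1 makes the list a condition for counting, the narrowing changes the outcome definition. A complication that the plan itself regards as relevant is counted when coded vaguely and can be dropped when coded exactly.

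The starred metrics would then run low. For a rate judged against a fixed ceiling, a low count works in favour of success. Section 6.3 does not say that the national average behind the ceiling was built with this list, so the trial's rate and its benchmark may not count the same events. Thrombosis is also the kind of event that aims 2a and 3a hope to prevent or detect early, so losing such events removes information from the comparison of the arms on these metrics.

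**Working it through.** **1. What the list admits.** The plan states no figure on this point, so there is none to reproduce. The check is of the text.

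- Heading of the row: lower-extremity deep-vein thrombosis in general.
- Content of the row: one sub-item limited to unspecified site, two single codes, no range.
- Comparison with other rows: the prosthesis-complication row uses a range (T8481XA-T8486XA), as does the wound-disruption row (T8130XA-T8132XA). The gastrointestinal-hemorrhage row lists three separate forms. The list therefore uses families of codes elsewhere, but not here.
- ED supplement: no thrombosis code among the additions.

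**2. Direction.** Let N be the events that a complete list would count, and M the events whose only qualifying diagnosis is a thrombosis coded to a named vein. The plan's list counts N − M. Since M ≥ 0, the observed rate (N − M)/n cannot exceed N/n. The same holds for cost, which sums the claims retained.

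**3. Effect of one missed admission on the <4% threshold.** Section 6.3 does not state the denominator. Section 4.1 gives 200 per group and 400 in total.

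- n = 200: 0.04 × 200 = 8. So 7/200 = 3.5% passes and 8/200 = 4.0% fails. One event is 1/200 = 0.5 percentage points.
- n = 400: 0.04 × 400 = 16. So 15/400 = 3.75% passes and 16/400 = 4.0% fails. One event is 1/400 = 0.25 points.

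With either denominator, a complete count that just fails becomes a pass if one admission is missed.

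**4. Sensitivity, on assumed inputs.** The full rate and the share of events not counted are both assumptions; the documents give neither. Expected observed rate = full rate × (1 − share). The last column is the exact binomial probability of 7 or fewer events in 200 at that rate.

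| Full rate (assumed) | Share uncounted (assumed) | Expected observed rate | P(observed <4%) |
|---|---|---|---|
| 4.5% | 0% | 4.5% | 0.32 |
| 4.5% | 5% | 4.275% | 0.38 |
| 4.5% | 10% | 4.05% | 0.44 |
| 4.5% | 20% | 3.6% | 0.57 |
| 5.0% | 0% | 5.0% | 0.21 |
| 5.0% | 5% | 4.75% | 0.26 |
| 5.0% | 10% | 4.5% | 0.32 |
| 5.0% | 20% | 4.0% | 0.45 |

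At a full rate of 4.5%, 200 × 0.045 = 9 events are expected, so a 10% loss is 0.9 of an admission and a 20% loss is 1.8. The table shows how sensitive the threshold is to a loss of one or two events. It does not estimate the loss.

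**5. Reach.** Section 4.1 lists 90-day readmissions, reoperations and ED visits with no code restriction. The potentially-preventable metric in section 6.1 reviews all events for their relation to the index procedure. The primary endpoint in sections 4.3 and 4.5 is the PPE-15. None of these depends on the row.

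**The case against.** The strongest reply has four parts.

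*Scope.* A reader might infer that these thromboses are lost from every readmission and ED outcome of the trial. The documents do not support that. The restriction covers only the three starred metrics. The 90-day counts in section 4.1 and the all-events review can still capture the cases, and section 4.5 describes no analysis of the starred metrics. This part stands and limits the point.

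*Other routes into the count.* An event qualifies through any listed code in first or second position, such as pulmonary embolism or a complication of the prosthesis. The row also holds two codes, and the table as read does not show whether the sub-item label describes both. So not every named-vein thrombosis is lost, and the rates may turn out unchanged. This stands: equal or lower is supported, certain understatement is not. It does not supply a listed entry for a thrombosis at a named site.

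*Size.* A reader might put a figure on the loss. For example, assume that 1% to 2% of an arm (2 to 4 patients) have a thrombosis admission and that 50% to 90% of these are coded to a named vein. Then 2 × 0.5 = 1 to 4 × 0.9 = 3.6 events are lost, or 0.5 to 1.8 points of 200. The arithmetic is right, but both inputs are assumed, and it further supposes no overlap with other listed codes. It is not a finding about this trial.

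*Bias between arms.* A reader might infer that the omission favours JointCOACH. Nothing in the documents supports that, since the same list serves both groups. Likewise, if the three prior years behind the cost threshold in section 6.3 are extracted with the same list, both sides of that comparison carry the omission. No threshold is shown for the ED rate. The exposed conclusion is therefore mainly the fixed hospitalization ceiling.

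**Conclusion.** The point holds for the 30-day hospitalization rate, the 30-day ED visit rate and the 90-day cost. Followed as written, the list treats as unrelated a lower-extremity deep-vein thrombosis coded to a named vein when no other listed code is first or second diagnosis. The three metrics are then equal to or lower than they would be with a complete list.

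The direction rests on the plan's own row label and counting rule. The size is unknown. What can be said is that one missed admission moves the rate by 0.5 points in an arm of 200, or 0.25 points in 400, and can turn a fail into a pass at the <4% threshold. That the threshold applies to a single arm is an assumption.

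The primary endpoint is untouched and the omission does not by itself tilt the randomized comparison. It merits correction because it is a stated counting rule that contradicts its own heading and is easily repaired before extraction.

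**What to change.** Before data extraction, replace the row's content with the code family for acute lower-extremity deep-vein thrombosis at any site, in place of the unspecified-site entries alone. If the narrow form was intended, say so and give the reason. Check the remaining rows for the same restriction to unspecified forms. Fix one final list, and use it for both arms and for any prior-year comparator to which the list is applied, so that the change does not create a new mismatch. State the denominator of the <4% threshold at the same time.

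The cost is a revised table, and possibly slightly less favourable observed rates. If the change is left until after extraction, it will be hard to show that it was not driven by the data.

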### 6.3 Success Thresholds for Study Metrics

Metric	Threshold	Rationale
Patient reported (0) satisfaction	$\geq 70\%$ satisfied or very satisfied	Value is consistent with most of the Medicare value based purchasing programs. 70% also exceeds thresholds targeted by several other large health systems.
Patient engagement	$\geq 70\%$ of members are $\geq 60\%$ engaged with the Joint Coach software	
Physician satisfaction	$> 80\%$ physician satisfaction	
Total 90 day post-operative cost (claims submitted) from index date+1 (same day) or from index date + LOS (inpatient)	No increase in cost during pilot study relative to cost averaged across 3 prior years (costs to be adjusted for inflation using either the medical care component of the Bureau of Labor Statistics Consumer Price Index, or The health system internal inflation index if available.)	Standard inflationary cost adjustment in medical economics is the medical care component of the CPI, or using a 3% discount rate.
30-day post-op hospitalization rate	$< 4\%$ considering the UHC national average	
30-day ED visit rate		
Number of follow up visits within 90 days		
Potentially preventable admissions		

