### **3. Specific Aims**

Currently in use by orthopedic groups around the country, JointCOACH improves perioperative outcomes after THA and TKA and mitigates risk by: 1) enhancing patient engagement with providers, 2) allowing patients to play an integral role in patient-reported outcomes, 3) generating and relaying actionable pre- and postoperative reporting directly to the clinical team, and 4) detecting impending postoperative complications early, enabling timely intervention and preventing avoidable complications and readmissions. The specific aims of this proposal are to:

1. Measure patient satisfaction with and without use of JointCOACH as a tool for patient engagement
2. Understand the degree to which high postoperative engagement can reduce the amount of healthcare resource utilization by answering the following questions:

- a. Will the use of JointCOACH decrease the number of potentially avoidable healthcare utilization encounters such as Emergency Department (ED) and hospital visits (i.e. readmissions and reoperations)?
  - b. Does utilizing JointCOACH improve clinical workflow by minimizing telephone calls and thereby offloading support staff, allowing them to be more efficient?
  - c. Does utilizing JointCOACH reduce the volume of on-call pages by addressing patient questions up front, alleviating concerns, and providing them with the information they need when they need it?
  - d. Does utilizing JointCOACH allow the practice to identify patients whose in-person follow-up needs are minimal?
3. Measure additional potential benefits including shorter length of hospital stay, discharge disposition to home rather than a facility and decreased 90 day readmissions and reoperations by answering the following:
  - a. Does utilizing JointCOACH lead to early detection of adverse signs/symptoms that develop between clinical encounters and result in reduced readmissions and reoperations?
4. Evaluate the financial impact of JointCOACH in the episode of care (% difference in Charges between JointCOACH and standard of care groups)

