## **4. Methods**

### **4.1 Study Design**

The study design is a prospective, randomized trial in which patients undergoing elective primary hip or knee arthroplasty will be offered perioperative use of JointCOACH vs standard of care. A total of 400 patients will be enrolled (200 in each group). The following outcome measures will be collected at the intervals specified in the Schedule of Events:

- Demographics (Age, gender, BMI)
- Comorbidities (Age-Adjusted Charlson Comorbidity Index)
- Surgical details (ASA (or other comorbidity index), Length of surgery (incision to closure), procedure type, operative limb, surgeon)
- Length of hospital stay and discharge disposition
- Number of ED visits and follow-up visits within 90 days
- Number of phone calls and on-call pages within 90 days
- Readmissions and reoperations within 90 days
- Patient satisfaction (VAS satisfaction and PPE-15)
- Provider satisfaction (5-point Likert scale)

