Potentially preventable readmissions and complications identified using JointCOACH	Potentially preventable admissions, events, ED visits. Using an approach similar to 3M's Potentially Preventable Events grouping software, we will examine all events (ED visits, admissions, complications) for relation to index event, and compare this rate to prior year. Data may be supplemented by Physician survey. http://solutions.3m.com/wps/portal/3M/en_US/Health-Information-Systems/HIS/Products-and-Services/Products-List-A-Z/PPR-and-PPC-Grouping-Software/

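### Aim 4 promises a randomised comparison of charges that Section 4.5 never specifies, while the metric tables judge cost, preventable events and hospitalization against prior years or a fixed 4%

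*Combined protocol and SAP*

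**What the plan says.** **Design and aim.** Section 4.1 describes a randomised trial: "A total of 400 patients will be enrolled (200 in each group". Section 3, Aim 4, sets the financial question as a contrast between those groups: "Evaluate the financial impact of JointCOACH in the episode of care (% difference in Charges between JointCOACH and standard of care groups". Aim 3 adds 90-day readmissions and reoperations.

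**Analysis.** Section 4.5 covers one outcome, the PPE-15 problem percentage, with a two-sample t-test. It says nothing about charges, cost, hospitalization or preventable events.

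**Data collected.** Section 4.1 lists "Readmissions and reoperations within 90 days" along with ED visits, calls, length of stay and satisfaction. Neither that list nor the Section 4.4 schedule has a charge or cost item.

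**Metric and threshold tables.**
- Cost (Section 6.3): "No increase in cost during pilot study relative to cost averaged across 3 prior years". The adjustment for inflation uses the medical care component of the CPI, or an internal index if there is one. The rationale column adds "or using a 3% discount rate".
- What counts as cost (Section 6.1): "Claims submitted within 90 days must be limited to ICD-10 listed below". Counting starts after the index day or the index stay.
- Preventable events (Section 6.1): "we will examine all events (ED visits, admissions, complications) for relation to index event", and then "compare this rate to prior year".
- 30-day hospitalization (Section 6.3): under 4%, set with reference to a national average. Section 6.1 restricts it to the listed ICD-10 codes and counts admissions after outpatient procedures.

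**The concern.** The trial pays for a concurrent randomised control. For cost, preventable events and hospitalization, though, the only decision rules written down look outside the trial. Someone following the document literally would have a rule for comparing cost with earlier years, but no method for the comparison that Aim 4 names.

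Three things are at stake. First, a prior-year contrast carries differences in patients and in calendar time as well as any effect of the tool, and the bias can go either way. Second, an absolute limit on hospitalization can be met or missed whatever the control group shows. Third, with two financial definitions and two readmission definitions in the plan, the choice of which to report could be made after the data are seen.

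**Working it through.** **1. Is there a plan figure to reproduce?** Only one sample size is computed, 153 per group for PPE-15 (Section 4.3). It follows from 2 × (1.960 + 0.842)² × 7.7² / 2.47² = 152.6, rounded up to 153, where 2.47 is 10% of 24.7. It does not bear on this point. No size, variance or power is given for cost, hospitalization or preventable events.

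**2. Comparators side by side.**

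| Outcome | Comparator in the aims | Comparator in 6.1/6.3 | Analysis in 4.5 |
|---|---|---|---|
| Charges / cost | Standard-of-care arm (Aim 4) | Mean of 3 prior years, inflation-adjusted | None |
| Preventable events | With or without JointCOACH (Aims 2a, 3a) | Prior year | None |
| Hospitalization | As above, 90 days (Aim 3) | Fixed, under 4% at 30 days | None |
| Satisfaction | With or without JointCOACH (Aim 1) | At least 70% satisfied | By-arm t-test (PPE-15) |

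**3. What a prior-year contrast measures.** Observed change = JointCOACH effect + case-mix difference + calendar trend (+ error in the inflation adjustment, for cost).
- *Case mix:* trial patients need internet or mobile access and a valid email address, and must not have a planned discharge to a skilled nursing facility. The prior-year cohort is undefined, so nothing says it is restricted in the same way.
- *Population:* if the rule is applied to all 400, only 200/400 = half were assigned JointCOACH, so a given effect on mean cost is halved.
- *Inflation:* the mean adjustment over three prior years is [(1+r) + (1+r)² + (1+r)³]/3. At an assumed 2% a year this is 1.0405, and at an assumed 4% it is 1.0822. The ratio is 1.040, so that gap moves the bar by 4.0%. The documents give no index values.

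The randomised contrast removes the case-mix and trend terms in expectation and needs no inflation index.

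**4. What meeting the 4% limit shows.** Under 4% means at most 7 events in 200, or at most 15 in 400. Exact binomial probability of meeting it when JointCOACH has no effect, at assumed true rates:

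| True rate | 2% | 3% | 4% | 5% |
|---|---|---|---|---|
| n = 200 | 0.951 | 0.746 | 0.450 | 0.213 |
| n = 400 | 0.992 | 0.848 | 0.465 | 0.150 |

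The result mainly reflects the underlying rate.

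**5. Definitions.**
- *Financial:* Aim 4 uses charges over the episode of care. Sections 6.1 and 6.3 use claims limited to listed codes and counted after the index stay. The second measure leaves out the index stay, so it cannot show a saving from the shorter stay that Aim 3 looks for.
- *Readmission:* Section 4.1 uses 90 days with no code limit. Sections 6.1 and 6.3 use 30 days with a code limit.

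**6. Precision of the by-arm comparison, 200 per arm.**
- Hospitalization at an assumed 4% in both arms: half-width 1.96 × √(2 × 0.04 × 0.96 / 200) = 0.0384, or 3.8 points. Power for an assumed 4% versus 2%, two-sided 5%: about 22%.
- Ratio of mean costs: log half-width 1.96 × CV × √(2/200) = 0.196 × CV. If 5% or 10% of patients have a qualifying claim, with CV 0.5 among them, the overall CV is √(1.25/p − 1) = 4.90 or 3.39. Taking CV 3 to 5 gives 0.588 to 0.980, a factor of 1.80 to 2.66 either way. An assumed CV of 0.5 for total charges gives 0.098, about ±10%. All these CVs are assumptions.

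**The case against.** The strongest reply is that Section 6.3 holds benchmarks and not the analysis. Its satisfaction threshold sits beside a by-arm test in Section 4.5, so in the one domain where the plan does specify an analysis, a threshold and a randomised comparison coexist. That supports a supplementary reading, and no text says that the thresholds replace the arm comparison. This stands, and it makes the confounding argument conditional on the rules being reported as the result. It does not supply the missing analysis for Aim 4 or reconcile the definitions.

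A reader might infer that no stated comparator uses the randomised control. That goes too far: Aim 4 itself names the standard-of-care group. The gap is between that aim and the rest of the plan.

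A reader might also infer that the cost rule is little better than a coin toss. The documents do not support that as a specific finding. Almost any no-increase rule against a known mean passes about half the time when nothing changes, and the plan gives no cost variance from which to say more.

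On inflation, the 3% rate appears only in the rationale column, and the words about availability partly govern the choice of index. The basis is therefore loosely specified, not contradictory.

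Finally, Section 2 calls this a pilot study, and the by-arm estimates will be imprecise. That is true, and it argues for intervals instead of tests. It is not a reason to rely on an undefined historical cohort.

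**Conclusion.** The concern holds in a limited form and should be fixed. Three parts rest on the text alone: Aim 4 has no stated analysis and no listed data item; cost and readmission are each defined in two ways; and the role and population of the Section 6.3 thresholds are not stated. Confidence in these is high.

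The bias argument is conditional. It applies if the prior-year rules are reported as evidence of effect, and its direction and size cannot be worked out from the documents. The probabilities for the 4% limit are exact given the assumed true rates, which the plan does not supply. The inflation and cost-precision figures are illustrations under stated assumptions.

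The PPE-15 primary comparison and its sample size are not affected. Blank threshold cells in Section 6.3 are not counted as a fault, since table text may have been lost.

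**What to change.** 1. **Section 4.5:** add by-arm comparisons of charges (Aim 4), preventable events, 90-day readmissions and reoperations (Aim 3), and the 30-day hospitalization metric. Report each as a difference, or a ratio of mean charges, with a 95% confidence interval. Use the same definitions in both arms and find events from records; the name of the preventable-event metric ties identification to JointCOACH, which control patients do not have.
2. **Sections 4.1 and 4.4:** add charges as a collected item.
3. **Aim 4 and Sections 6.1/6.3:** state one cost definition and window for Aim 4. Keep the 90-day unrestricted and 30-day code-restricted readmission measures as separately named outcomes.
4. **Sections 6.1/6.3:** label the prior-year and 4% figures as descriptive benchmarks. State whether they apply to the JointCOACH arm or to all 400, define the prior-year cohort's eligibility, and name one inflation index. The other thresholds can stay.

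**Cost:** text edits, plus charge extraction for up to 400 patients, which Aim 4 already implies. No extra patients or visits. The price is wide intervals, especially for code-restricted cost, so these outcomes should be reported as estimates without a pass/fail conclusion.

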### Exclusion criteria

1. Staged arthroplasty procedure within 6 months of the index procedure

2. Abandoned email address of record (e.g. bounce of email from clinic)
3. Planned discharge to a Skilled Nursing Facility

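### The under-4% success line for 30-day hospitalization refers to an undefined national average, but the trial's rate counts only listed codes in a selected sample, so the two are not shown to be comparable

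*Combined protocol and SAP*

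**What the plan says.** - **Threshold (6.3).** The 30-day post-operative hospitalization rate must be below 4%, "considering the UHC national average". The rationale cell for that row is empty. The row gives no year, population or numerator rule for the average, no arm and no confidence limit.
- **Numerator (6.1).** The metric covers readmission after an inpatient index procedure and admission after an outpatient one. Its footnote restricts it: "Must be associated with ICD-10s listed below in order to exclude unrelated readmissions".
- **Code position (6.2).** For an admitted patient, the listed code must be in the first or second "diagnosis on hospital discharge". The list covers device and wound complications, infection, bleeding and venous thromboembolism. Fever and sepsis codes and some DRGs follow, after the remark "Since ED coding is often not as precise as the above, we will likely need to also have these below".
- **Sample (4.2).** Exclusions include "Planned discharge to a Skilled Nursing Facility" and "Staged arthroplasty procedure within 6 months of the index procedure". Inclusion requires internet or mobile access and a valid email address.
- **Data collected (4.1, 4.4).** Readmissions are recorded and tracked with no code filter stated.

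**The concern.** A threshold taken from an external average is informative only if the trial's rate is built the same way. Here the trial's rate passes through a filter whose declared purpose is to remove hospitalizations from the count, and through eligibility rules that select the sample. Nothing in the documents says that the external figure went through either.

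Reducing readmissions is a named aim (section 3, aims 2a and 3a). The under-4% line is also the only numeric pass mark for a utilization event in 6.3, because the cells for ED visits, follow-up visits and preventable admissions are blank. A pass is likely to be read as doing better than the national average. If the average counts more kinds of hospitalization than the trial does, a pass would not support that reading.

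**Working it through.** **The plan's own figure.** The 4% cannot be reproduced. The documents give no source value, definition or derivation for it. What can be checked is how the rule behaves if the benchmark is not restricted to the 6.2 codes.

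**Inputs from the documents.** 200 patients per arm (4.1, 4.3); success means a rate below 4% (6.3); only listed-code hospitalizations count (6.1, 6.2).

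**Assumptions.** The rule is applied to the 200 JointCOACH patients. R is the true 30-day rate counting all hospitalizations. f is the share of them that meet the code rule. The documents do not give f, so a range is shown.

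**Step 1: the pass mark in events.** 7/200 = 3.5% passes. 8/200 = 4.0% does not. Success is therefore 7 or fewer counted events.

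**Step 2: overall rate that sits at the line.** The counted rate is R × f, so the line corresponds to R = 4% / f: 4.0% at f = 1, 4.4% at f = 0.9, 5.0% at f = 0.8 and 8.0% at f = 0.5.

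**Step 3: probability of passing.** P(pass) = P(X ≤ 7), with X binomial (n = 200, p = R × f).

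| True overall rate R | f = 1 | f = 0.9 | f = 0.8 | f = 0.5 |
|---|---|---|---|---|
| 4% | 0.45 | 0.57 | 0.69 | 0.95 |
| 5% | 0.21 | 0.32 | 0.45 | 0.87 |
| 6% | 0.08 | 0.15 | 0.25 | 0.75 |

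For example, R = 6% and f = 0.8 give p = 0.048 and P(X ≤ 7) = 0.25.

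**Step 4: separating two weaknesses.** The f = 1 column has no code mismatch, yet a true 5% still passes with probability 0.21, because the rule uses a point estimate alone. The mismatch accounts for the rise from that column. At R = 5% and f = 0.8 the rise is 0.45 − 0.21 = 0.24.

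**Step 5: dependence on the arm.** If the rule is applied to all 400 patients, 15 or fewer events pass (15/400 = 3.75%; 16/400 = 4.0%). At R = 6% the pass probability is 0.03 at f = 1, 0.20 at f = 0.8 and 0.85 at f = 0.5. The pattern is the same.

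**Step 6: precision at the pass mark.** A passing 7/200 has an exact 95% CI of about 1.4% to 7.1%, which extends well above 4%.

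**The case against.** The strongest reply is that the benchmark is not described. The average may be complication-related, and 4% need not equal it: the wording also fits a cut-off set lower to allow for a narrower numerator. This stands. A reader might infer that the rule is lenient by construction, or that only the trial's side is narrowed. The documents do not support either, because they show one side of the comparison only.

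Three further inferences are tempting and also go too far.

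- **That the hospitalization code list is unsettled.** The remark about probably needing more codes opens with imprecise ED coding, and the ED visit rate is a separate metric in 6.1. If the fever, sepsis and DRG rows do apply to admissions, they widen the count and raise f.
- **That the net direction is known.** Section 6.1 also counts admissions after outpatient surgery. If the benchmark covers readmissions only, the trial's count is broader in that respect.
- **That eligibility lowers the rate by some amount.** Excluding planned Skilled Nursing Facility discharges plausibly lowers it, but the documents give no rates for excluded patients and do not say that the benchmark includes them.

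It is also fair that f has no anchor in the documents, and that this is one appendix row with no stated action tied to it. The only specified test is on the PPE-15, and a randomized comparison of readmissions does not need the benchmark.

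None of this shows that the two rates are comparable. Followed as written, the rule can report success against a line not shown to match the rate, although a concurrent randomized control arm is available.

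**Conclusion.** The concern holds in conditional form. The under-4% line and the rate judged against it are not shown to be the same quantity. If the average is not restricted to the 6.2 codes, the threshold can be met when the comparable rate is at or above 4%.

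The size is illustrative. At a true overall rate 1.5 times the threshold, the chance of passing rises from 0.08 to 0.15 if only one hospitalization in ten falls outside the code rule, and to 0.75 if half do. This rests on 200 JointCOACH patients, an unrestricted benchmark and an assumed f. If the benchmark used the same code rule, the numerator part would vanish. The true size, and any contribution from sample selection, cannot be determined from the documents.

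The change is worth making, but it concerns an appendix success metric. The PPE-15 primary endpoint is unaffected.

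**What to change.** In 6.3, change the row for 30-day hospitalization as follows.

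1. Make the concurrent standard-of-care arm the comparator. Both arms pass through the same eligibility rules and the same code rule, so neither difference from an outside population matters.
2. Report two rates by arm: any 30-day hospitalization without a code filter, and the 6.2-coded rate. Give an exact 95% CI for each rate and a 95% CI for the difference between arms.
3. Use the 4% line only as a descriptive reference, and only beside a rate built with the benchmark's own numerator rule. State the benchmark's definition, population and year. Simply moving the line to any-cause hospitalization is not safe, because it presumes an all-cause benchmark and could create the reverse mismatch.
4. State in 6.2 whether the fever, sepsis and DRG rows apply to hospitalizations or only to ED visits.

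**Cost.** A little more analysis, and possibly a less favourable figure against 4%. Readmissions are already collected without a stated code filter (4.1, 4.4). Admissions after outpatient surgery must be captured too, as 6.1 already requires. The between-arm estimate will be imprecise: with 4% in each arm, the standard error of the difference is √(2 × 0.04 × 0.96 / 200) = 0.0196, so the 95% CI is roughly ±3.8 percentage points. Item 3 needs the benchmark's definition from its source; if that cannot be obtained, drop the reference line.
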